9.3 DEFINITION OF AN UNEXPECTED ADVERSE EVENT

An **unexpected** adverse event is any adverse event, the specificity or severity of which is not consistent with information in the clinical protocol or current Investigator's Brochure for an

	Protocol No.: SciB018
	Version and Date: Version 2.0, September 9, 2015 Amendment 1

unapproved investigational product or package insert/summary of product characteristics for an approved product (package inserts are available separately at the participating center).

Suspected Unexpected Serious Adverse Reaction (SUSAR) is a serious adverse reaction assessed as unexpected by the Sponsor and that is judged by either the reporting investigator or the Sponsor to have a reasonable causal relationship to a medical product.

9.4 NOTIFICATION OF SERIOUS OR UNEXPECTED ADVERSE EVENT

Per FDA new safety reporting requirements (US Department of Health and Human Services September 2010)³⁰ a sponsor must continue to “promptly” review all safety information obtained from foreign or domestic sources. However, the sources of information listed in the regulation has expanded to include “any clinical or epidemiological investigations, animal or *in vitro* studies, reports in the scientific literature, and unpublished scientific papers, as well as reports from foreign regulatory authorities and reports of foreign commercial marketing experience for drugs that are not marketed in the United States.

If the Investigator identifies an SAE or Unexpected AE, an SAE report form must be completed and sent within 24 hours of the Investigator’s knowledge of the event to the sponsor. The names (and corresponding telephone numbers) of the individuals who should be contacted regarding safety issues or questions regarding the study are listed on the Contact Information page(s), which will be provided as a separate document.

These preliminary reports will be followed within 24 hours by more detailed descriptions that will include a completed SAE form, copies of hospital case reports (i.e., hospital progress notes, results of applicable diagnostic tests, lab results and biopsy results), autopsy reports, and other documents, when requested and applicable.

For regulatory purposes, initial SAE reports submitted to SciVac immediately and should include:

- a) a suspected investigational medicinal product
- b) an identifiable subject (e.g., study subject code number)
- c) an adverse event with a seriousness and the Investigator’s assessment of the relationship to study drug
- d) an identifiable reporting source (investigator contact details)

Once faxed or emailed, the printed SAE form and accompanying documentation should be placed in the SAE section of the Investigator’s site file.

In addition, all AEs/SAEs/SUSARs will be reported to the IRB/IEC and regulatory authorities as required by local regulations and ICH-GCP guidelines.

Follow-up of SAEs/SUSARs

Follow-up of SAEs/SUSARs that occur during the study will continue until their satisfactory resolution or stabilization. In outstanding cases, it may be defined as “ongoing without further follow-up” by the Investigator and Sponsor’s decision.

When supplementary information is available, a follow-up SAE Report Form must be completed by the site (marked as “follow-up report”) and reported as indicated above.

	Protocol No.: SciB018
	Version and Date: Version 2.0, September 9, 2015 Amendment 1

Information to include on SAE form

The following information should be provided in the SAE form to accurately and completely record the event:

Investigator name and site address
 Subject study identification number
 Subject's initials
 Subject demographics (gender, date of birth or age, weight, height)
 Clinical Event:

- Description
- Date and time of onset, stop date, or duration
- Severity
- Treatment (including hospitalization)
- Relationship to study drug (causality)
- Action taken regarding study drug
- Information on recovery and any sequelae
- If the AE resulted in death
 - Cause of death (whether or not the death was related to study drug)
 - Autopsy findings (if available)
- Medical History case report form (copy)
- Concomitant Medication case report form (copy)
- Any relevant reports (laboratory, discharge, etc.)

Accompanying documentation, such as copies of hospital case reports, autopsy report, and other documents when applicable, should be sent as soon as they are available.

Subsequent additional information (follow-up) about any SAE unavailable at the initial reporting should be forwarded by the site to the Sponsor representative and study monitor within 24 hours of the information becoming available.

SAEs should also be reported to the IRB/IEC according to local regulations.

Subjects who have had an SAE during the treatment period must be followed clinically until all parameters (including laboratory) have either returned to normal or have stabilized or are otherwise explained.

Any newly emergent SAE after treatment is discontinued or the subject has completed the study and is considered to be related to the study drug or study participation should be recorded and reported immediately. The post-study period for the purpose of SAE reporting is up to 30 days following last visit of the study.

Follow-up Reports for non-serious AEs

All AEs, that do not meet any of the criteria for serious, should be regarded as non-SAEs. All AEs must be followed until resolution or stabilization and will be recorded on the Adverse Event Record in the CRF and if relevant, the Concomitant Medications Record in the CRF. Severity and relationship to study drug will be assigned by the Investigator as described in the section above.

	Protocol No.: SciB018
	Version and Date: Version 2.0, September 9, 2015 Amendment 1

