Pregnancy and Nursing Mothers: Animal reproduction studies have not been conducted with the vaccine. It is also not known whether the vaccine can cause fetal harm when administered to a pregnant woman or can affect reproduction capacity. The vaccine should be given to a pregnant woman only if clearly needed. It is not known whether the vaccine is excreted in human milk. Since many drugs are excreted in human milk, caution should be exercised when the vaccine is administered to a nursing woman.

Pediatric Use: Sci-B-Vac has been shown to be well tolerated and highly immunogenic in infants and children of all ages. Newborns also respond well; maternally transferred antibodies do not interfere with the active immune response to the vaccine.

Adverse Reactions

Sci-B-Vac is generally well tolerated. No serious adverse reactions attributable to the vaccine have been reported during the course of clinical trials. As with any vaccine, there is the possibility that broad use of the vaccine could reveal adverse reactions not observed in clinical trials.

In a series of studies, 2313 doses of Sci-B-Vac were administered to 771 healthy adults who were monitored for 5 days after each dose. The following adverse reactions were reported:

Incidence Equal to or Greater Than 1% of Injections:

Local Reaction (Injection Site): Injection site reactions consist of soreness and include pain, tenderness, pruritus, erythema, ecchymosis, swelling, warmth and nodule formation. These reactions were mild and resolved within two days after vaccination.

Additional complaints included fatigue/weakness, headache, fever (37.8°C), malaise, nausea, diarrhea pharyngitis and upper respiratory infection.

Incidence Less Than 1% of Injections:

Sweating, aching, sensation of warmth, light-headedness, chills, flushing, vomiting, abdominal pains/cramps, dyspepsia, diminished appetite, rhinitis, influenza, cough, vertigo/dizziness, paresthesia, pruritus, rash (non-specified), angioedema, urticaria, arthralgia including monarticular, myalgia, back pain, neck pain, shoulder pain, neck stiffness, lymphadenopathy, insomnia/disturbed sleep, earache, dysuria and hypotension.

Dosage and Administration

Sci-B-Vac is a sterile suspension for intramuscular injection.

Adult Formulation, 10 µg/ml: each 1 ml dose contains 10 µg hepatitis B surface antigen; recommended for children above the age of 10 years and adults.

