	
3. The geometric mean concentration (GMC) as determined by anti-HBsAg antibody titers at Month 0, then at every month until Month 7 inclusive and at months 9 and 12.
 
Exploratory endpoints:
 
 • The anti-preS1 antibody titers measured at Month 0, then at every month until Month 7 inclusive and at months 9 and 12. • The anti-preS2 antibody titers measured at Month 0, then at every month until Month 7 inclusive and at months 9 and 12.

Study Design and Procedures
	
This is an open label, single arm, single center clinical study in healthy subjects, who were never vaccinated against Hepatitis B and who are HBs antigen, anti-HBc and anti-HBsAg antibodies seronegative.
 
Eligible subjects will be vaccinated 3 times with 10 mcg/ml of Sci-B-Vac™ according to the immunization schedule.
 
The study will consist of three periods:
 
 • Screening period: Up to 4 weeks prior to first vaccination • Treatment and follow-up period: 6 months • Post-vaccination follow-up period: 6 months 
Blood samples will be collected prior to the first vaccination (Month 0), every month until month 7 inclusive, at Month 9 and at Month 12.
 
Safety parameters will be assessed as outlined below and in Section 6.4.

Duration of Study (Clinical Stage)
	
The duration for an individual subject is approximately 13 months.

Number of Subjects
	
Up to 84

Inclusion Criteria
	
 1. Healthy males and females between 20 and 40 (inclusive) years of age. 2. Subjects who provide written informed consent to participate in the study. 3. Subjects in general good health in the opinion of the investigator as determined by medical history, vital signs and a physical examination. 4. No clinically significant abnormalities in hematology, blood chemistry, or urinalysis lab tests at screening. 5. Women of child-bearing potential must practice an acceptable method of birth control or practice abstinence during the study period or be surgically sterilized, from screening visit throughout the treatment phase and for 28 days after the last injection and agree to undergo repeated pregnancy tests. 6. Subjects must be able to understand the requirements of the study and must be willing to comply with the requirements of the study.

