6.1.7 Visit 7 – Follow-up: Month 5 (Week 20 \pm 3 days)

Procedures will be identical to Visit 4.

6.1.8 Visit 8 - Third Vaccine Administration: Month 6, (Week 24 \pm 3 days)

The third (last) vaccination will take place 5 months after the second vaccination (Visit 3). The previous injection site will be inspected before the third administration. Procedures will be identical to Visit 2, except the volume of blood drawn for serology, safety laboratory testing and for further investigational purposes, which will be lower (35 ml).

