6.1.11 Visit 11 – Study Termination: Month 12 (Week 48 \pm 8 days)

The following assessments will be performed:

- Physical examination
- Vital signs: (sitting BP, HR, RR, oral temperature)
- 12-lead ECG
- Laboratory safety tests (See Appendix B)
- Serology tests

	Protocol No.: SciB018
	Version and Date: Version 2.0, September 9, 2015 Amendment 1

- Blood samples for additional investigational purposes
- AE and concomitant medication recording

The amount of blood drawn in this visit is approximately 28 ml

The total amount of blood drawn for serology and routine safety laboratory tests will be about 424 ml over a period of 13 months.

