9 SAFETY AND PHARMACOVIGILANCE

9.1 ADVERSE EVENT DEFINITION

An AE is defined as "Adverse event means any untoward medical occurrence associated with the use of a drug in humans, whether or not considered drug related".

An AE (also referred to as an adverse experience) can therefore be any unfavorable and unintended sign (e.g., an abnormal laboratory finding), symptom, or disease temporally associated with the use of a drug, without any judgment about causality or seriousness. An adverse event can arise from any use of the drug (e.g., off-label use, use in combination with another drug) and from any route of administration, formulation, or dose, including an overdose.

An abnormal result of diagnostic procedures including abnormal laboratory findings will be considered an AE if it fulfills one or more of the following:

	Protocol No.: SciB018
	Version and Date: Version 2.0, September 9, 2015 Amendment 1

- Results in subject's withdrawal by the Investigator
- Is associated with a serious adverse event (SAE)
- Is associated with clinical signs or symptoms
- Is considered by the physician to be of clinical significance (a laboratory abnormality that is not clinically significant will not be considered an AE)

A new condition or the worsening of a pre-existing condition will be considered an AE.

An adverse reaction means any adverse event caused by a drug. Adverse reactions are a subset of all suspected adverse reactions for which there is reason to conclude that the drug caused the event.

Suspected adverse reaction is “any adverse event for which there is a reasonable possibility that the drug caused the adverse event.”

AEs do not include the following:

- Stable or intermittent chronic conditions (such as myopia requiring eyeglasses) that are present prior to study entry and recorded in the subject's file and do not worsen during the study
- Medical or surgical procedures (e.g., surgery, endoscopy, tooth extraction, transfusion). The condition that leads to the procedure is an AE if not present at baseline
- Overdose of either study drug or concomitant medication without any signs or symptoms unless the subject is hospitalized for observation
- Hospitalization for elective surgery planned prior to study (situation where an untoward medical occurrence has not occurred)
- Pregnancy alone is not considered an AE. Elective abortions without complications should not be handled as AEs.

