9.2 SERIOUS ADVERSE EVENTS (SAEs)

An SAE is any AE occurring at any dose that suggest a significant hazard or side effect, regardless of the Investigator or Sponsor's opinion on the relationship to the investigational product and that results in, but may not be limited to, any of the following outcomes:

- death (regardless of the cause)
- a life-threatening adverse event or suspected adverse reaction
- inpatient hospitalization or prolongation of existing hospitalization (any inpatient hospital admission that includes a minimum of an overnight stay in a health care facility)
- a persistent or significant disability/incapacity or a substantial disruption of the ability to conduct normal life functions
- a congenital anomaly or birth defect
- Important medical events that may not result in death, be life-threatening, or require hospitalization may be **serious** when, based upon appropriate medical judgment, they may jeopardize the subject and may require medical or surgical intervention to prevent one of the outcomes listed above.

Inpatient hospitalization or prolongation of existing hospitalization means that hospital inpatient admission and/or prolongation of hospital stay were required for treatment of AE, or that they occurred as a consequence of the event.

Hospitalization for elective treatment of a pre-study condition that did not worsen while on study and optional hospitalizations not associated with a clinical adverse event (e.g., elective cosmetic surgery) are not considered SAEs.

Significant medical events are those which may not be immediately life-threatening, but may jeopardize the subject and may require intervention to prevent one of the other serious outcomes listed above. Examples of such events are intensive treatment in an emergency room or at home for allergic bronchospasm; blood dyscrasias or convulsions that do not result in hospitalization; resulting in an AE will normally be considered serious by this criterion.

A **life-threatening** adverse drug experience is any adverse event that places the subject, in the view of the Investigator, at immediate risk of death from the reaction as it occurred, i.e., it does not include a reaction that, had it occurred in a more severe form, might have caused death.

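### The 30-day post-study SAE period does not cover term-birth outcomes of pregnancies conceived around dose 3, and Protocol Version 2.0 section 9 requires no pregnancy report or outcome follow-up

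*Protocol*

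**What the plan says.** All references are to Protocol Version 2.0 unless stated.

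- Section 9.2 includes "a congenital anomaly or birth defect" among the outcomes that make an event serious.
- Section 9.1, on what does not count as an AE: "Pregnancy alone is not considered an AE. Elective abortions without complications should not be handled as AEs".
- Section 9.4 makes an SAE that arises after treatment or completion reportable if it is related: "Any newly emergent SAE after treatment is discontinued or the subject has completed the study and is considered to be related to the study drug" (the text adds study participation as an alternative). It then limits the period: "The post-study period for the purpose of SAE reporting is up to 30 days following last visit of the study".
- The product leaflet (Appendix D of Version 1.0; section 9.5 of Version 2.0 still relies on the leaflet) says: "It is also not known whether the vaccine can cause fetal harm when administered to a pregnant woman or can affect reproduction capacity".
- Timing: "Third Vaccine Administration: Month 6, (Week 24" with a window of 3 days either side (section 6.1.8), and "Study Termination: Month 12 (Week 48" with a window of 8 days either side (section 6.1.11).
- Women aged 20 to 40 are eligible (section 5.2). Urine pregnancy tests are done before each injection and at Month 12 (section 4.1; SAP 2.3). SAP Table 14.3.4-7 tabulates the results.

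Section 9 does not say what follows a positive test.

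**The concern.** A birth defect is normally recognised at or after delivery, so this SAE criterion works only if someone is still asking when the baby is born. The plan tests for pregnancy at four visits, but an uncomplicated pregnancy opens neither an AE nor an SAE record. The duty in 9.4 to follow SAEs to resolution therefore never starts. If the reporting period also ends before delivery, a study report could state that no congenital anomaly occurred when, for pregnancies conceived around the last dose, no procedure was in place to see the birth. The leaflet calls fetal risk unknown, so that statement would matter to a reader. No efficacy endpoint or estimate is affected.

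**Working it through.** **Inputs from the documents.** Dose 3 is at week 24, plus or minus 3 days. The last visit is at week 48, plus or minus 8 days. Post-study SAE reporting lasts 30 days. Days are counted from dose 1 as day 0. The last visit is taken to be the subject's own.

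**Assumption not in the documents.** Term birth is at 37 to 42 completed weeks from the last menstrual period, with conception at two weeks. That is 35 × 7 = 245 to 40 × 7 = 280 days from conception.

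**Plan's own figure.** The synopsis states "Post-vaccination follow-up period: 6 months". Week 48 − week 24 = 24 weeks = 168 days, which is six four-week study months (about 5.5 calendar months). The figure is reproduced.

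**Length of the SAE period after dose 3** = (last visit − dose 3) + 30:

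- nominal: (336 − 168) + 30 = 198 days, closing on day 366
- longest (dose 3 three days early, last visit eight days late): 179 + 30 = 209 days
- shortest (the reverse): 157 + 30 = 187 days

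**Conception on the day of dose 3.** Days from close to term birth:

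| SAE period | Birth at 245 days | Birth at 280 days |
|---|---|---|
| nominal, 198 days | 47 | 82 |
| longest, 209 days | 36 | 71 |
| shortest, 187 days | 58 | 93 |

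At the nominal close the pregnancy is at 198 + 14 = 212 days, or 30 weeks 2 days.

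**Conception near dose 3.** Conception 14 days earlier puts a 37-week birth 245 − 14 − 198 = 33 days outside (22 with the longest period). Conception 28 days later puts it 245 + 28 − 198 = 75 days outside (64 with the longest). For a 37-week birth to fall inside, conception must precede dose 3 by at least 245 − 198 = 47 days (36 with the longest).

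**Six calendar months in place of 24 weeks.** The period is 183 + 30 = 213 days, or 224 with the windows at their limit. A 37-week birth from conception at dose 3 is still 245 − 224 = 21 days outside.

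**Doses 1 and 2.** Conception on day 0 gives a term birth on days 245 to 280. Conception on day 28 gives days 273 to 308. Both precede day 366 for a woman who stays to about Month 12.

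**The case against.** **The reporting rule is not a prohibition.** A reader might infer that a later anomaly could not be reported. The documents do not say so. Section 9.4 starts its 24-hour clock at the investigator's knowledge of the event and also refers to local regulations. What is missing is a duty to find out.

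**A pregnancy may still reach the sponsor.** Section 8.2 expects urine tests to stay negative during the study, and section 11.7 requires protocol deviations to be reported to the sponsor. A positive test may arrive by that route, so it would be wrong to say that the sponsor would never learn of a pregnancy. Neither section asks for the outcome. Section 5.7 asks for every effort at safety follow-up after withdrawal, but gives no duration and does not mention the newborn.

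**Pregnancies at dose 3 should be few.** Contraception is required and a urine test precedes each injection, although a test can miss a very recent conception. The documents give no expected number, so none is offered here. Rarity makes the remedy cheap; it does not supply the follow-up.

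**Parts of the plan are not visible.** Version 2.0 was available only up to section 11.8. The SAP plans 92 subjects against 84 and says that its flow chart follows protocol changes, so later protocol text probably exists. The SAP listings appendix was also not available, and its version history adds listings 16.2.8-7-2 and 16.2.8-7-3, whose content is unknown. The statement that no duty exists is therefore limited to section 9 of Version 2.0, which is complete.

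**The last visit could mean the last subject's.** Earlier subjects would then have a longer period, but the last-enrolled women would not. The preceding sentence in 9.4 speaks of a subject who has completed the study, which favours the subject's own visit.

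**Conclusion.** The point holds for term births from conceptions around dose 3. On the day of dose 3 the gap is 47 to 82 days nominally and 36 to 93 days across the visit windows. It does not close anywhere in the assumed range of 245 to 280 days, nor on the calendar-month reading. It rests on that assumed range and on reading the last visit as the subject's own.

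Three stronger readings are not supported:

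- **That the trial could observe no congenital anomaly at all.** One found prenatally or at a preterm delivery could fall inside the period.
- **That all exposed pregnancies are missed.** Those conceived near doses 1 and 2 are inside in time for women who stay to about Month 12, although section 9 does not require their follow-up either.
- **That a woman found pregnant is withdrawn and her period closes within weeks.** Pregnancy is not among the discontinuation reasons in section 5.6. It is true only that anyone who leaves early, for whatever reason, has an earlier close on the subject's-own-visit reading.

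This is a safety-reporting gap that should be closed.

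**What to change.** In sections 9.1 and 9.4:

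1. Keep pregnancy as a non-AE.
2. Require any pregnancy found from first dose to the end of the SAE period, including at the Month 12 test, to be sent to the sponsor on a pregnancy form within 24 hours.
3. Require follow-up of each such pregnancy to its outcome, including the newborn's status.
4. Exempt congenital anomaly and pregnancy loss in those pregnancies from the 30-day limit.

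In the SAP, add a listing of pregnancies and outcomes beside Table 14.3.4-7, unless an existing listing already gives it.

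Separately, the contraception end points differ: 28 days after the last injection in inclusion criterion 5 (section 5.2), and the end-of-study visit in section 8.2. The two passages must be reconciled, because they determine whether conception during the remaining follow-up is foreseen.

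The cost is one form, one or two contacts for each woman concerned, and a few sentences of text. The drawback is that a small number of records may close after the main report and need an addendum. The change concerns reporting and follow-up only.
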